## Introduction

This statistical analysis plan (SAP) documents the planned statistical analyses for the CHANCE study and is based on the protocol, together with any subsequent amendments.

This SAP is intended for the use of project team members within Beijing Tiantan Hospital, and should be read in conjunction with the aforementioned protocol.

## Study Objective(s) and Endpoint(s)

### Study Objective(s)

The primary objective of this study is to assess the effects of a 3-month regimen of clopidogrel initiated with a loading dose of 300 mg followed by 75 mg/day combined with aspirin 75 mg/day during the first 21 Days versus a 3-month regimen of aspirin 75 mg/day alone on reducing the 3-month risk of any stroke (both ischemic and hemorrhagic) when initiated within 24 hours of symptom onset in high-risk patients with TIA or minor ischemic stroke.

The secondary objectives of this study are:

- To assess the secondary composite outcome: composite of any stroke, myocardial infarction, and vascular death
- To assess separately the effects of this Clopidogrel regimen versus ASA alone on the incidence of: new clinical vascular events (ischemic stroke/ hemorrhagic stroke/ TIA/ MI/ vascular death) as a cluster and evaluated individually.
- To assess whether there are differential treatment effects in predefined subgroups:
  - ✧ (<65 years vs ≥65 years)
  - ✧ Sex (male vs female)
  - ✧ Index event (minor stroke vs TIA)
  - ✧ TIA risk stratification ( $ABCD^2=4$  vs  $ABCD^2>4$ )
  - ✧ Previous stroke
  - ✧ Previous TIA
  - ✧ History of hypertension
  - ✧ History of diabetes
  - ✧ Systolic blood pressure at baseline (<140mmHg vs ≥140mmHg)
  - ✧ Time to randomization (<12 hours vs ≥12 hours)
  - ✧ Aspirin taken within 24h
- To assess the primary outcome measure in a Per-protocol (PP) population. This will include all patients who have not had a significant interruption of study drug (less than a total of 10 days off study drug) or major protocol violation.

Other objectives are:

- To evaluate treatment differences if changes in modified Rankin Scale from baseline to the last follow-up.
- To compare the safety of the two treatment regimens in terms of:
  - ✧ Severe or moderate bleeding (GUSTO definition)
  - ✧ Intracranial hemorrhage
  - ✧ Total mortality
  - ✧ AEs/SAEs

- In further exploratory analysis, to evaluate treatment differences of impairment (change in NIHSS scores), and Quality of Life (EuroQol EQ-5D scale) among survivors.

### Study Endpoint(s)

#### **Primary Efficacy**

- Rate of new stroke (both ischemic and hemorrhagic) reported during the 3-month treatment period.

#### **Secondary Efficacy**

- Rate of the composite outcome: including any stroke, myocardial infarction, and vascular death as a cluster and evaluated individually

#### **Other Efficacy**

- Changes of the Modified Rankin Scale scores between the end of study and baseline.
- Further efficacy exploratory analysis:
  - ✧ Changes in NIHSS scores between the end of study and baseline.
  - ✧ Changes in EuroQol EQ-5D scale between the end of study and baseline.

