#### 4.6.2 Secondary Efficacy Endpoint

- Percentage of composite of any stroke, myocardial infarction, and vascular death within 3 month.
- Patients with the 3-month new clinical vascular events (ischemic stroke/ hemorrhagic stroke/ TIA/ MI/ vascular death) evaluated individually.
- Modified Rankin Scale score changes (continuous) and dichotomized at percentage with score 0-2 vs. 3-6 at 3 month follow-up (Scale is described in Appendix 2).
- Further efficacy exploratory analysis:
  - ✧ Impairment (changes in NIHSS scores at 3 month follow-up), (Scale is described in Appendix 3).
  - ✧ Quality of Life (EuroQol EQ-5D scale, described in Appendix 4).
- Efficacy endpoint will also be analyzed stratified by etiological subtypes (non-ICAD vs. ICAD), by time randomization (< 12 hours vs. ≥ 12 hours), by qualifying event (TIA vs. minor stroke), and by age (<65 years vs. ≥65 years).

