#### 9.1.2 Baseline Evaluation

Baseline evaluation will include patient demographic information, symptoms of the index event, medications, past medical history, family history, cigarette and alcohol use, examination findings, pretreatment Rankin Score.

Laboratory tests will be performed (serum creatinine, glycemia, neutrophil count (or at least a total WBC count) and platelet count)

A physical examination will be performed, including measurement of weight (kg) and vital signs (supine systolic and diastolic blood pressure, heart rate)

Results of head imaging, CBC, and ECG will be recorded using standardized instruments.

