### **9.3 Three month Visit = D 90±7**

**Note: Number of days between D21±2 and D 90±7 visits may not exceed 75 days.**

During this visit:

- ✓ If the patient will be diagnosed by sICAD, MRI+MRA (MRI including T1 + T2 + DWI + FLAIR + T2\*) sequences will be strongly encouraged to perform. Images will be transferred to the core imaging evaluation lab.
- ✓ A neurological evaluation will be performed (Modified Rankin Scale and NIHSS)
- ✓ Quality of life scale (EQ-5D) will be performed in a quiet room (Appendix 4)
- ✓ A physical examination will be performed, including vital signs (supine systolic and diastolic blood pressure, heart rate)
- ✓ Information will be collected on concomitant medications and adverse events since the last visit
- ✓ The treatment box from completed study period with unused study medication will be collected for drug accountability and assessment of treatment compliance

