### **10.2.2 Secondary Outcomes**

The analysis strategy outlined for the primary outcome will be used for most of the secondary analyses. For continuous outcomes (such as NIHSS and mRS), we will use a multiple linear regression analysis. Continuous outcomes will be checked for approximate normality and heteroscedasticity of residuals and for outliers. Transformations and/or weighted least squares will be considered as remedies for non-normality and heteroscedasticity. Outliers will be checked for validity and their influence on conclusions will be tested in sensitivity analyses.

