### Other Efficacy Analyses

#### **Disability measure**

Changes of the modified Rankin Scale (mRS) between the end of study and baseline will be summarized for the two treatment groups among the survivors during the study. The treatment difference will be tested using student t-test.

---

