## Quality of life

Health related quality of life will be measured using EuroQol EQ-5D scale among the survivors. Treatment differences will be tested using student t-test.

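### The SAP lists an EQ-5D change from a baseline that is never collected, and it replaces the protocol's mRS 0-2 vs 3-6 endpoint with a survivor-only t-test of mRS change

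*Supplement*

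**What the plan says.** **EQ-5D.** The final SAP, under Other Efficacy, lists "Changes in EuroQol EQ-5D scale between the end of study and baseline". Its later Quality of life paragraph says "Health related quality of life will be measured using EuroQol EQ-5D scale among the survivors" and compares the arms by t-test; the word change does not appear there. In the final protocol, the schedule of assessments (section 1.2) marks EQ-5D once, at the Day-90 visit. Section 9.3, the three-month visit, states: "Quality of life scale (EQ-5D) will be performed in a quiet room (Appendix 4". Section 9.1.2 begins "Baseline evaluation will include patient demographic information, symptoms of the index event, medications, past medical history, family history, cigarette and alcohol use" and goes on to examination findings, pretreatment Rankin score, laboratory tests and vital signs, without EQ-5D. The Day 1 list (9.1.4) and the Day 21 visit (9.2) do not include it either.

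**mRS and NIHSS.** Protocol section 4.6.2 makes mRS a secondary efficacy endpoint in two forms: a continuous change, and a split "dichotomized at percentage with score 0-2 vs. 3-6 at 3 month follow-up". Objective 3.2.4 likewise asks for the percentage scoring 0-2. Section 10.2.2 gives the method: "For continuous outcomes (such as NIHSS and mRS), we will use a multiple linear regression analysis". The SAP places mRS under Other Efficacy as a change score only. Its Disability measure paragraph says that changes "between the end of study and baseline will be summarized for the two treatment groups among the survivors during the study", tested by Student t-test. The NIHSS paragraph follows the same pattern.

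**The concern.** Three things do not fit together.

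1. A listed endpoint needs a baseline value that no visit collects.
2. A protocol secondary endpoint has no analysis, although protocol section 10.1 leaves it to the SAP to define every planned, pre-specified analysis.
3. Protocol and SAP name different methods for the same scales.

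The survivor rule for mRS adds a bias question. Survival is determined after randomisation and may depend on treatment. An mRS comparison restricted to survivors is therefore no longer a comparison of the randomised groups, and it leaves out the worst outcome on the disability scale.

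If this stays open until the data are unblinded, the team will have to redefine EQ-5D and choose an mRS analysis with the results in view.

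**Working it through.** The plan states no figure on this point, so the check is mainly a comparison of texts.

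**Step 1: can the EQ-5D change be computed?** It needs a baseline value and a Day-90 value. The schedule and section 9 supply only the second, and the schedule in the Chinese final protocol agrees. The answer is no. A Day-90 comparison, as the SAP's Quality of life paragraph describes it, can be computed.

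**Step 2: where does mRS 0-2 vs 3-6 appear?**

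| Item | Final protocol | Final SAP |
|---|---|---|
| Status of mRS | Secondary (4.6.2) | Other Efficacy |
| Continuous change | Yes | Yes |
| 0-2 vs 3-6 | Yes (4.6.2; 0-2 also in 3.2.4) | Absent |
| Survivors only | Not stated for mRS; stated for NIHSS and EQ-5D (3.2.10) | Yes, for mRS, NIHSS and EQ-5D |
| Method for mRS and NIHSS | Multiple linear regression (10.2.2) | Student t-test of change |

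The scale printed in protocol Appendix 2 ends at grade 5, while the endpoint runs to 6. Grade 6 can reasonably only mean death, but that is an inference; the protocol does not define it.

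**Step 3: how many patients does the survivor rule remove?** The documents give no expected mortality, so Day-90 mortality m is assumed. With 2550 per arm (protocol 10.1.1.1.6), deaths removed per arm = 2550 × m.

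To size the effect on the mean, assume equal mRS change among survivors in both arms, a mean baseline mRS of 0.5, death scored 6, and a death ratio between arms of 0.5 or 1.5. The hidden difference is then m × 0.5 × (6 − 0.5).

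To size the effect on the split, assume 5% or 10% of patients are alive at mRS 3-5. The share of deaths in the 3-6 category is then m/(m + 0.05) or m/(m + 0.10).

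| m | Deaths removed per arm | Hidden mean difference, mRS points | Share of 3-6 that are deaths (10% / 5% alive at 3-5) |
|---|---|---|---|
| 0.5% | 12.75 | ±0.014 | 4.8% / 9.1% |
| 1% | 25.5 | ±0.028 | 9.1% / 16.7% |
| 2% | 51 | ±0.055 | 16.7% / 28.6% |

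**Step 4: what does a change-score t-test cost in precision?** Let r be the correlation between baseline and Day-90 scores, and k the baseline SD divided by the Day-90 SD. The variance ratio of the change score to an analysis of covariance is (1 + k² − 2rk)/(1 − r²). The documents give neither r nor k.

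| r | k = 1 | k = 0.5 |
|---|---|---|
| 0.2 | 1.60/0.96 = 1.67 | 1.05/0.96 = 1.09 |
| 0.3 | 1.40/0.91 = 1.54 | 0.95/0.91 = 1.04 |
| 0.5 | 1.00/0.75 = 1.33 | 0.75/0.75 = 1.00 |

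**The case against.** **These are minor endpoints.** The SAP classes mRS change as other efficacy and the remaining two scales as exploratory. The primary endpoint, sample size, composite and safety conclusions do not depend on them. This stands, and it sets the severity.

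**EQ-5D remains usable.** A reader might infer that the quality-of-life analysis is lost. It is not: the SAP's analysis paragraph can be carried out with the Day-90 value, and neither the SAP objectives nor the protocol's endpoint list calls for an EQ-5D change. The fault lies in one endpoint line that contradicts the rest.

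**Deaths are counted elsewhere.** A reader might infer that they disappear from the plan. They do not. The SAP has a Cox model for all-cause death and a Fisher's exact test for deaths, vascular death is in the composite, and a fatal stroke counts in the primary endpoint. The gap is confined to the disability comparison, where the protocol wanted a category reaching 6. For NIHSS and EQ-5D, the restriction to survivors is the protocol's own wording in 3.2.10, so the SAP does not depart from it there.

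**The bias in the mean is small.** Under the assumptions above it is at most 0.055 points. This stands for the mean; deaths weigh more in the 0-2 vs 3-6 split.

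**The precision loss may be negligible.** Equal SDs would give a ratio of 1.33 to 1.67, equivalent to discarding 25% to 40% of patients. A reader might take that as the expected loss. Entry excludes mRS above 2 and NIHSS of 4 or more, so a smaller baseline SD is plausible, and the ratio can then be close to 1. Efficiency alone does not carry the point.

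**The regression text differs by language.** The Chinese section 10.2.2 also prescribes multiple linear regression for continuous outcomes but gives other examples than mRS and NIHSS. The conflict in method is therefore explicit in the English text only.

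**Conclusion.** The point holds in this form: the EQ-5D change endpoint cannot be computed and contradicts the SAP's own analysis paragraph; the protocol's mRS 0-2 vs 3-6 endpoint has no SAP analysis; the mRS comparison that replaces it leaves out deaths; and the t-test conflicts with the English protocol's regression for mRS and NIHSS. All of this follows from the texts, apart from reading grade 6 as death.

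The sizes rest on assumptions. With Day-90 mortality of 0.5% to 2%, about 13 to 51 patients per arm drop out of the mRS comparison, and deaths would form about 5% to 29% of the 3-6 category. The variance ratio of change score to analysis of covariance is about 1.0 to 1.1 if the baseline SD is half the Day-90 SD, and 1.33 to 1.67 if the SDs are equal, for r of 0.2 to 0.5.

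This should be fixed. It is not critical, because the primary endpoint and its conclusions are unaffected.

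**What to change.** Before database lock and unblinding:

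- **EQ-5D:** define the endpoint as the Day-90 value and remove the reference to change, in line with the SAP's Quality of life paragraph.
- **mRS split:** add the Day-90 analysis of 0-2 vs 3-6 in the ITT population, name the model and effect measure, and count deaths in 3-6. Define grade 6 as death in protocol Appendix 2.
- **mRS and NIHSS as continuous scores:** replace the t-tests of change with regression of the Day-90 score on treatment and the baseline score, consistent with protocol 10.2.2. Keep survivor-only mRS as supportive.
- **NIHSS and EQ-5D among survivors:** these may stay as the protocol's exploratory analyses. Giving deaths a value there is optional.

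The cost is SAP wording, one line in the appendix and a few lines of code. Day-90 scores, baseline mRS and NIHSS, and deaths are already collected, so no visit or form changes.

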#### **Safety Endpoint**

- Rate of moderate and severe bleeding incidence (GUSTO definition), including fatal bleeding and symptomatic intracranial hemorrhage
- Rate of symptomatic and asymptomatic intracranial hemorrhagic events at 3 months
- Rate of total mortality
- Incidence of AEs/SAEs (as described in the protocol) reported by the investigators

Clinical safety will be assessed by a physical examination including neurological evaluation at Day 1, D21 and D90 visits. Adverse events will be collected at each visit after baseline. Supine blood pressure and heart rate will be measured at each visit. No specific laboratory safety tests are required during this study. However, if a laboratory abnormality is clinically relevant or leads to an adverse event report, specific appropriate actions may be required (see Appendix 5, decision charts). An ECG will be performed at the baseline visit (Day 1).

### Statistical Hypotheses

The primary endpoint for this study will be the rate of new stroke (both ischemic and hemorrhagic) reported during the 3-month treatment period.

The null hypothesis of no difference in this rate between the two treatment groups will be tested using a two-sided test at the 5% level of significance

$$H_0: \lambda_1/\lambda_2 = 1$$

$$H_1: \lambda_1/\lambda_2 \neq 1$$

Where  $\lambda_1$  is the rate of new stroke over the 3-month treatment period in the group treated with Clopidogrel/ASA regimen and  $\lambda_2$  is the same endpoint in the group treated with ASA alone.

### Study Design

The primary null hypothesis of this randomized, double-blind multicenter clinical trial is, there is no difference in 90-day risk of any new stroke (ischemic or hemorrhagic) in those treated with a 3-month regimen of clopidogrel initiated with a loading dose of 300 mg followed by 75 mg/day combined with

aspirin 75 mg/day during the first 21 Days versus a 3-month regimen of aspirin 75 mg/day alone when initiated within 24 hours of symptom onset in high-risk patients with TIA or minor stroke..

Patients with high-risk TIA (defined as an ABCD score  $\geq 4$ ) or minor ischemic stroke (defined as an NIHSS  $\leq 3$ ), who can be treated within 24 hours of symptom onset will be enrolled. Patients meeting these criteria and offering informed content will be randomized into two groups: the first group will receive a 300mg loading dose of clopidogrel on the day of randomization, followed by 75 mg clopidogrel/day from Day 2 to 3 months. Aspirin will be given in a total dose ranging between 75 mg and 300 mg (open label with dose determined by the treating physician) on the first day, followed by blinded 75 mg once /day from Day 2 to 21. Between day 22 and 3-month visits, aspirin 75 mg will be replaced by a placebo of aspirin 75 mg. The second group will receive open label aspirin in a total dose ranging between 75 mg and 300 mg on the first day, followed by 75 mg once/day from Day 2 to 3 months. A placebo for clopidogrel will be given from the day of randomization until the 3-month visit. Subjects will be followed for 90 days and risk of any stroke (ischemic or hemorrhage) will be assessed in the treatment groups. The trial will be completed in 35 months, with 5,100 subjects recruited from about 100 centers in China in partnership with research network and CHANCE Clinical Research Collaboration. A Data and Safety Monitoring Board (DSMB) will regularly monitor safety during the study.

### **Planned Analyses**

The analyses that are detailed in this SAP will be performed only when the database has been frozen, all protocol violators identified and treatment allocations have been unblinded. The treatment allocations will be unblinded and extracted from the RandAll system. These will then be merged on to the study database using the treatment number (as allocated to each subject by RAMOS) to match subjects with the correct treatment allocation. Membership of the Intent-to-Treat and Per Protocol populations will be determined using the rules set out in this SAP and will be determined prior to unblinding the treatment allocation. At a date to be agreed within the project team, a data look will be performed. This will involve production of all data displays on a subset of the data using dummy treatment codes. These are produced purely as an aide to the pre-programming of the study and no unblinding will occur.

### **Interim Analyses**

No interim analyses are planned for this study. However, a Data and Safety Monitoring Board (DSMB) is in place to ensure the safety of subjects in the study. An independent statistician will prepare unblinded summary tables of SAEs, selected demographic data and subject exposure data and these will be examined by the DSMB. These tables will be provided to the DSMB at regular intervals. If the tables give rise to safety concerns for any treatment, the DSMB may recommend that the trial should be modified or stopped prematurely. The Steering Committee will, in conjunction with the Sponsor, decide whether to act on this recommendation. Further discussion of these safety tabulations is provided in a specific study protocol.

---

## **Sample Size Considerations**

Sample size for the study assumed that the number of new stroke events ( ischemic or hemorrhagic) would follow a Poisson distribution. The rate of new stroke events was expected to be 0.14 per subject within 3-month after Day 1 in the ASA alone treated group based on a previous study. It was expected that the Clopidogrel/ASA treated group would reduce this by 22%; this is equivalent to 0.11 exacerbations per subject within 3-month after Day 1. With this relative risk reduction, treatment of 32 patients with TIA or minor stroke (regardless of other risk factors) would be expected to rescue one stroke event over 3 months. With a sample size of 5100 patients, we will have 90% power to detect a relative risk reduction of 22% with a two-sided alpha of 0.05, and 5% drop outs (medication non-adherence).

## **Analysis populations**

### **Total Population**

This population will comprise of all subjects screened and for whom a record exists on the study database. This population will be used for listing adverse events occurring prior to randomization and reasons for withdrawal occurring prior to randomization.

### **Intent-to-Treat Population**

The Intent-to-treat (ITT) population will comprise of all subjects Randomized to treatment and who received at least one dose of trial medication. Randomized subjects will be assumed to have received trial medication unless definitive evidence to the contrary exists.

The ITT Population will be used for tables of efficacy, demography, safety, health outcomes, listings of withdrawals after randomization, and all relevant listings. This population will be the primary population for analyses of efficacy and safety.

### **Per Protocol population**

The Per Protocol (PP) population will consist of all subjects in the ITT population not identified as protocol violators. The decision to exclude a subject from the PP population will be made prior to breaking the blind. This population will be used for secondary analyses of the primary efficacy measure. The decision to exclude a subject from the Per Protocol Population will be made prior to breaking the study blind. A partial protocol violator will be included in the Per Protocol Population up to the time of their violation. For the Per Protocol Population, subjects will be analyzed according to the treatment received, providing the same treatment was taken for the duration of the study. If study medication was changed then the subject will be considered a partial protocol violator (from the point of change onwards).

---

## **Treatment comparisons**

The treatment comparison of interest in this study is between clopidogrel /ASA combination followed by clopidogrel alone regimen and an ASA alone regimen over the 90-day treatment period, based on the ITT population.

## **General considerations for data analyses**

All programming will be performed using SAS Version 9.0. All analysis output will use the following treatment group naming conventions and treatment order:  
clopidogrel /ASA for a loading dose of clopidogrel 300mg followed by clopidogrel 75 mg /day day 2-90 plus blinded aspirin 75 mg once /day day 2-21 and then aspirin placebo day 22-90  
ASA for clopidogrel placebo on day 1, followed by aspirin 75 mg/day plus clopidogrel placebo day 2-90  
Unless otherwise specified all significance tests will be 2-sided at the  $\alpha=0.05$  level and all confidence intervals will be 95%.

